
Intervention

The following key intervention components will be implemented: An orientation of how to use the HIV self-test kit will be provided, with printed instructions left with two self-test kits. Self-testing kits will NOT

be provided to a couple if only one member of the couple agrees to the test and to disclosure. This measure will be employed to protect the safety of clients and avoid potential coercive testing. We will utilize the OraSure OraQuick® Rapid HIV-1/2 test kit for self-testing. Couples will also be instructed on how to take universal precautions when handling the test (latex gloves will be provided) and what to do with the test once it is used (either by disposing of it themselves, returning it to the Study Center during confirmatory testing for later incineration, or placing it in a sealed envelope to be collected by data collectors who will return two weeks following self-test kit provision). The couple will be instructed that if either of the couple members has a positive HIV test that they should go to the **Study Center** we establish, together as a couple if possible. The couple will also be instructed to come to the Study Center if they receive an equivocal test result or have trouble interpreting the results (standard testing using the Tanzanian National Testing Algorithm will be conducted). We will also give them the phone number of the center, so they can also call or text if they have questions. Following self-testing, counselors will be available to participants at the Study Center. Participants can also reach counselors by phone during operating hours (a phone number will be provided to them prior to self-testing). This service will be provided in addition to the standard counseling that will be available once participants report to the Study Center. No personal information will be divulged via phone when calls are made. For participants who contact the center, have had a positive test, but are unable to come to the center we will offer to come back to their house to consult with them. If only one member of the couple presents at the center, they will be offered services, but we will seek permission to contact the other member of the couple for follow up. The Study Center will be located within walking distance to the Kisarawe Care and Treatment Center (CTC), which is centrally located in the study area, and fairly easy for participants to access either by walking or bicycle. The CTC is operated by the District Health System, is located in the Kisarawe District Hospital, and is funded with support from PEPFAR.

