Protocol for Mitigating Risks – Importantly, there are some key safety considerations associated with the use of HIV self-test kits and the collection of biometric data. Prior to commencing study enrollment, we will develop a detailed safety protocol. Fortunately, multiple members of the research team (Drs. [name] and [name]) have extensive experience managing safety risks in research, and [name],⁶⁵⁻⁷¹ is an expert in the study of interpersonal violence. Specific to the provision of HIV self-test kits, there is the possibility that one partner might attempt to coerce the other partner to take the test. There is also the possibility for a loss of confidentiality of individual's HIV status. Finally, there is the potential for psychological distress or intimate partner violence if an individual's HIV status becomes known. Several strategies will be used to reduce these risks. To minimize risk for partner coercion, members of each couple will be consented separately in private. Further, when training research staff in the consenting procedures, it will be emphasized that under no circumstances should they or any household member attempt to influence an individual's participation. Prior to distributing test kits to a consented couple, staff will provide counseling to the couple to ensure both members are comfortable receiving the test and to develop an agreement regarding shared confidentiality. Finally, all study participants will be provided access to the study counselor located in the community.

Measures

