Data Structure: There are two key unique features of the primary data for this proposal. First, because couples are enrolled in the study, there is inherent nesting of two individuals within each couple. Second, the measurement design leads to repeated measurements outcomes for some of the aims. Given the aims of the study, many of the outcomes will be evaluated using descriptive statistics. However, issues such as nesting and repeated measurements will be carefully considered. For example, for the first aim, uptake will be reported by each individual within the couple, and the descriptive statistics will be reported both at the individual level within the couple and at the aggregate couple level. For the outcomes that will be evaluated using inferential statistical analyses, the nested data structures (e.g., repeated measurements within couples) will be addressed using mixed-effects regression models (MRMs; e.g.).⁸¹ These highly flexible models accommodate variability in the number/spacing of outcome measurements, and they readily accommodate linear and non-linear outcome distributions (e.g., dichotomous, count). **Outcome Distributions & Individual Trajectories:** Prior to analysis, each outcome will be carefully inspected to determine the most appropriate distribution for modeling. Likewise, for outcomes with repeated measurements, the trajectory for each participant on each outcome will be plotted using “spaghetti plots”.⁸² These plots will illustrate the level of and variability in each outcome, along with patterns of change over time. **Model Building & Estimation:** Singer and Willett’s (2003)⁸³ model building approach will be used to specify fixed and random effects. The MRMs will be performed using MLwiN software.⁸⁴ Due to the relatively modest sample size for some of the analyses, the models will also be performed using Bayesian MCMC-based estimation⁸⁵ in MLwiN. This simulation-based approach utilizes a large number of iterations – each informing the next – to produce an empirically-based sampling distribution for each parameter. For example, rather than a single point estimate of the parameter of interest, the MCMC-based provides the magnitude, precision, and variability of the parameter estimates. **Attrition & Missing Data:** Individuals or couples who drop out of clinic care will be retained, when possible, in ongoing research measurement according to Intention-to-treat principles.⁸⁶ Some research data will inevitably be missing, and the methods recommended by Schafer and Graham⁸⁷ will be used to evaluate missing data assumptions and guide the subsequent analyses. Given few missing data and evidence supporting a MAR mechanism, the procedures detailed above will be utilized with all available data. Given non-trivial missing data and evidence supporting MAR, multiple imputation for longitudinal data will be used to provide complete data.⁸⁸ Finally, given non-trivial missing data and evidence suggesting NMAR, pattern mixture models will be used to control the missing data.⁸²

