
Evaluation of Specific Aims & Associated Hypotheses

AIM 1 - We hypothesize that the majority of couples (GT ~ 50%) will utilize the HIV self-test kits and share their results with their partner. To evaluate the factors associated with uptake of HIV self-testing, a single level logistic regression model with a logit link function will be performed. The outcome will be the HIV self-testing status (0 = did not use self-test, 1 = used self-test). Demographic variables (e.g., age & gender) will be evaluated as predictors of self-testing uptake, with results focusing on ORs, and corresponding 95% CIs.

AIM 2 - We hypothesize that a large proportion of serodiscordant couples who present to the study referral office (GT ~ 70%) will engage in care together, have higher rates of adherence and retention than individually enrolled clients, and have a reduction in risk behaviors for HIV transmission from baseline to 18-month follow up. For this aim, there are repeated measurements of retention in care and adherence (level-1) nested within positive partners (level-2). A dichotomous predictor variable at the individual level (i.e., level-2) will test for differences in the log-odds of treatment retention between those enrolled in care as a couple and those enrolled in routine clinic services. The adherence outcome will be analyzed in a similar manner. For this outcome, there are several indicators of medication adherence. First, for the positive member of the couples, self-reports of ARV adherence will be obtained at 6, 12, and 18 months. Second, individuals on ARV are expected to return to the clinic each month to have the prescription refilled. Third, for individuals in the study, viral load tests will be obtained at 18 months allowing us to assess viral suppression as a marker for medication adherence. For the

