2. Moreover, the study and associated intervention is designed to target couples as a dyadic unit, and the vast majority of couples will be heterosexual and thus include a man and a woman. Both men and women will be recruited to participate in intervention services. All ethnic groups will be sampled for inclusion with no bias and should be proportional to their distribution in the population given the geographically based sampling being utilized.
3. HIV is highly prevalent among both men and women in the study communities. As such, the study intervention will offer Dyadic-based Diagnosis, Care, & Prevention (DDCP) services to members of both genders in an attempt to apply study findings to both males and females, and any minority groups present in the community.
4. No gender or ethnicity will be excluded from the trial.
5. The trial will seek to enroll members of both genders and individuals of any ethnicity residing in the study communities. The study team will assure that the Community Advisory Board has substantial members of both women and men, residing in the community.

Inclusion of Children

Children age 18-21 years (as defined by NIH guidelines) will be eligible to participate in the study. In Tanzania 18 years is the legal age at which an individual may independently consent to participate in clinical research. It is important that 18-21-year-olds are included in the proposed trial as young adults are the most at risk age group for contracting HIV. Our study personnel are experienced in conducting research with 18-21-year-olds as our previous and current studies have provided a host of HIV services, including HIV testing and counseling, to young adults and our staff are familiar with the specific risks affecting this age group in Tanzania.

Sources of Materials

Human subject materials will consist of demographic & behavioral survey data, and clinical data collected at the Care and Treatment Center (HIV test results, CD4 counts, medications prescribed and taken, and clinical observations) collected from subjects in the self-testing cohort, and at baseline, 6-months, 12-months, and 18-months for the approximately 120 individuals identified as being a member of a HIV serodiscordant couple), and from utilization data collected at each use of a service. In order to access this data, we will collect the Care and Treatment patient number of participants.

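### Aim 1's single-level logistic model ignores the pairing of partners, against the plan's own rule for nested data; if partners' test use is correlated, the gender CI is too wide and the age CI too narrow

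*Combined protocol and SAP*

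**What the plan says.** All references are to the combined protocol and SAP.

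- **Section D, Analysis Plan, Data Structure.** The plan notes that "because couples are enrolled in the study, there is inherent nesting of two individuals within each couple". It takes Aim 1 as its illustration, saying that "uptake will be reported by each individual within the couple", with descriptive results to be given for individuals and for couples. For inferential analyses, "the nested data structures (e.g., repeated measurements within couples) will be addressed using mixed-effects regression models".
- **Section D, Evaluation of Specific Aims, AIM 1.** "To evaluate the factors associated with uptake of HIV self-testing, a single level logistic regression model with a logit link function will be performed". This model predicts whether the self-test was used (yes or no). Demographic variables, with age and gender as the examples, are the predictors. Odds ratios with 95% CIs are the reported result.
- **Section E, Inclusion of Women and Minorities.** The plan expects that "the vast majority of couples will be heterosexual and thus include a man and a woman".

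Neither the Data Structure text nor the Aim 1 text gives this model a couple random effect, GEE, couple-clustered standard errors, or a restriction to one partner per couple.

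**The concern.** A single-level logistic model treats every record as independent. Here the records come in pairs, and there are good reasons to expect the two partners to behave alike. They live together, "staff will provide counseling to the couple to ensure both members are comfortable receiving the test" (Protocol for Mitigating Risks), and the orientation ends "with printed instructions left with two self-test kits" (Intervention). Kits are withheld unless both agree.

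Aim 1(a) asks which factors are associated with uptake, so these odds ratios and their CIs are the answer to a stated aim. Ignoring positive correlation pushes the two named predictors in opposite directions:

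- **Gender** varies within the couple, so the pairing makes its estimate more precise than the model reports. A real difference between men and women could be missed.
- **Age** is likely to be similar within couples, so its estimate is less precise than reported. A chance association could be declared.

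A reader of the results could not undo either error without knowing the within-couple correlation.

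**Working it through.** **Unit of analysis.** Gender cannot distinguish one man-woman couple from another. With gender as a predictor, the model must therefore use individuals: 884 (442 couples) to 2,000 (1,000 couples).

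**The plan's own figure.** The only Aim 1 precision figure concerns the uptake proportion (Precision of Estimates and Statistical Power): 46% to 54% for n = 442 at 50% uptake. The usual formula gives 50% ± 1.96 × √(0.25/442) = 50% ± 4.7 points, or 45.3% to 54.7%. That mismatch is a separate matter. The plan gives no figure for the regression, so there is none to reproduce.

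**Inputs not in the documents (assumed).** The within-couple correlation of test use, rho, is taken as 0.1, 0.3, 0.5 and 0.8. The correlation between partners' ages is taken as 0.8 or 0.5. The ICC of 0.50 in the power section is for repeated measurements on one person and does not apply to partners.

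**Formulas.** For clusters of two, with r_x the within-couple correlation of the predictor:

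- single-level SE ÷ correct SE = 1/√(1 + rho × r_x), with r_x = −1 for gender
- type I error = 2 × [1 − Φ(1.96 × ratio)]
- power where a correct analysis has 80% = Φ(2.80 − 1.96 × ratio), with 2.80 = 1.96 + 0.84

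Example at rho = 0.5. For gender the ratio is 1/√0.5 = 1.41, and 1.96 × 1.41 = 2.77 gives a type I error of 0.6%. For age with r_x = 0.8 the ratio is 1/√1.4 = 0.85, and 1.96 × 0.845 = 1.66 gives 9.8%.

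| rho | Gender: SE ratio | Gender: type I error | Gender: power (80% if correct) | Age, r_x 0.8: SE ratio | Age, r_x 0.8: type I error | Age, r_x 0.5: type I error |
|---|---|---|---|---|---|---|
| 0.1 | 1.05 | 3.9% | 77% | 0.96 | 5.9% | 5.6% |
| 0.3 | 1.20 | 1.9% | 68% | 0.90 | 7.8% | 6.8% |
| 0.5 | 1.41 | 0.6% | 51% | 0.85 | 9.8% | 8.0% |
| 0.8 | 2.24 | about 0% | 6% | 0.78 | 12.6% | 9.8% |

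**Simulation.** With 442 couples, 60% uptake, no true effects, partner-age correlation 0.8 and 4,000 replicates, the single-level model gave these type I errors at rho 0.1 / 0.3 / 0.5 / 0.8:

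- gender: 4.1 / 2.1 / 0.5 / 0.0%
- age: 6.2 / 8.2 / 9.9 / 11.9%

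Couple-clustered standard errors gave 3.9% to 5.6% throughout. A separate simulation (50% uptake, 2,000 runs, rho 0.5, age correlation 0.8) gave single-level CI coverage of 99.2% for gender and 90.5% for age. Clustering restored these to 94.6% and 95.5%. At rho = 0 the single-level coverage was 94.5% to 95.4%, so the distortion comes from the pairing.

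**Individual-level uptake.** The same issue arises if a CI is attached to the proportion among 884 individuals. The half-width is 1.96 × √(0.25 × (1 + rho)/884): 3.3 points if partners are taken as independent, and 3.5 / 3.8 / 4.0 / 4.4 points at the four values of rho.

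**The case against.** The strongest reply is that there is no real contradiction. The Aim 1 illustration in Data Structure is about descriptive statistics, and the only example attached to the mixed-model rule is repeated measurements. Single-level may simply mean that there are no repeated measures, as it does for the 18-month CD4 comparison. This is a fair reading of how the wording arose, but it does not help the analysis. The example is only an example, and couple nesting is listed as a feature in its own right, ahead of repeated measurement. On the narrow reading, the plan has no inferential method for the nesting that it calls inherent.

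A second reply is that the Aim 1 hypothesis and the stated precision are at couple level. That is true of both, but gender as a predictor rules out a couple-level regression.

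Several other points stand:

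- The size of the error rests on assumed correlations. With rho = 0 there is no error, and with uncorrelated partner ages there is none for age.
- The gender error is conservative, and the study is largely exploratory and descriptive.
- The plan computes no CI on 884 individuals; its n = 442 gives a wider interval (± 4.7 points) than any clustered value above. The uptake-proportion figures are therefore a side point.
- GEE or robust standard errors would also depart from the letter of the mixed-model rule, so that rule's wording needs adjusting too if they are chosen.

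**Conclusion.** The concern holds. As written, the Aim 1 model conflicts with the plan's rule for nested data and gives wrong CIs and tests whenever partners' test use is correlated; for age, partners' ages must be correlated as well. At assumed rho of 0.3 to 0.5, the type I error is 1.9% to 0.6% for gender, and 7.8% to 9.8% for age with partner-age correlation 0.8. Power for gender falls from 80% to between 68% and 51%. At rho = 0.1 the effect is small.

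The consequence is limited. The odds ratios remain valid population-average estimates, and the Aim 1 hypothesis about the proportion of couples who test and share results is not tested by this model. The single-level PrEP uptake model in Aim 3 is not affected, because each couple has only one negative partner. This should be corrected before analysis, but it does not threaten the study.

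**What to change.** Reconcile the Aim 1 paragraph with Data Structure:

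1. State that the model of individual self-test use has one record per partner and accounts for couple. Either use GEE or couple-clustered standard errors, which keep the population-average odds ratio, or use the random-intercept logistic model that Data Structure implies, which gives a couple-specific odds ratio.
2. Say which odds ratio will be reported. The choice is not cosmetic: for a small gender effect the couple-specific log odds ratio is about 1/(1 − rho) times the population-average one, that is 1.1, 1.4, 2 and 5 times at rho 0.1, 0.3, 0.5 and 0.8.
3. If GEE or clustered standard errors are chosen, word the Data Structure rule so that it allows them.
4. Use couple-clustered CIs wherever uptake is reported for individuals.
5. Analyse the couple-level outcome in the hypothesis (both partners used the kits and shared results) with one record per couple; a single-level model is adequate there.

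The core change is one or two sentences in the analysis plan and one software option. No new data are needed.

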first outcome, self-reported ARV adherence, the three repeated measurements will be nested within the positive partners. The unconditional model will estimate the rate of, and variability in, ARV adherence across participants. Based on inspection of "spaghetti plots," subsequent level-1 growth models will be specified to test for change in the rate of ARV adherence over time. For the second outcome, each positive individual from the study and from the CTC will have 18 monthly measurements of ARV refill status (i.e., 0 = Not Refilled, 1 = Refilled). This will be modeled as described above, with the level-2 dichotomous indicator testing for a difference in the average log-odds of adherence for those enrolled as a couple and those enrolled in routine clinic care. Given the large number of measurements per individual, alternative specifications are possible, and this will be guided by inspection of the spaghetti plots. For the third outcome, CD4 counts at 18 months will be compared using a single-level regression model to test for differences between those enrolled as a couple and those enrolled in routine services. For the fourth outcome, sexual frequency, condom use, and sex in the context of ARV or PrEP will be estimated. Using a mixed-effects model, predictor variables related to risk will be added to the model. These variables will also be considered for entry as time-varying covariates (i.e., entry at level-1) or as aggregative, couple-specific predictors.

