For AIM 2 - For the estimated sub-sample of 50 individuals for the PrEP use outcome, the 95% confidence interval for 50% PrEP use is 36% to 64%. If this percentage is as high as 75%, the confidence interval would be 63% to 87%. For the MRMs, this sample is sufficient for accurate estimates of fixed effects.⁸⁹ Although the point estimates of variance components and SEs could be biased, the proposed Bayesian MCMC-based analyses will provide increasingly valid estimates and will provide information about the variability and precision of the estimates.⁸⁵ Also of note, with the current design, the primary statistical test (i.e., that a time-varying correlation = 0) has a much smaller sample size requirement than does the primary statistical test for a traditional randomized design (i.e., between-group difference in slopes = 0). Statistical power was estimated using the method recommended by Maas and Hox⁸⁹ for a design with a level-1 predictor variable, a random intercept, and no other random effects. The lower limit on power is provided by the outcomes with 3 research measurement occasions, and outcomes utilizing clinic data and samples will offer much higher statistical power. With an estimated 50 individuals and 3 measurement occasions, the level-1 sample size is 150. Penalizing this sample for a nesting effect characteristic of repeated measurement data, ICC = .50, the effective level-1 sample size is 75 (i.e., given the dependence in the data, the level-1 sample of 150 offers the power of a sample of 75). For the dichotomous outcome and the dichotomous level-1 predictor, with an effective level-1 sample of 75, power is .80 to detect an event rate of 30%

(i.e., OR = 4.26). Assuming up to a 20% loss to follow-up rate, we will enroll 60 couples to ensure there are at least 150 measurements in total.

In sum, with between 442 and 1,000 couples in the HIV self-testing component of the study, and between 60-70 couples in the Dyadic Care component of the study we estimate that we will have adequate statistical precision and power to answer the requisite study questions.

TIMELINE – Based on experience working in the area we feel confident we can meet these goals:

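### If loss from care is nearly permanent, the repeated yes/no retention model gives a large, unstable, person-specific odds ratio; retention needs a definition and an 18-month or time-to-loss summary

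*Combined protocol and SAP*

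**What the plan says.** The AIM 2 text (Evaluation of Specific Aims & Associated Hypotheses) expects positive partners in couple care to "have higher rates of adherence and retention than individually enrolled clients". It states that "there are repeated measurements of retention in care and adherence (level-1) nested within positive partners (level-2", and that a dichotomous person-level predictor is used to examine "differences in the log-odds of treatment retention between those enrolled in care as a couple and those enrolled in routine clinic services". According to the Analysis Plan, nested structures "will be addressed using mixed-effects regression models", estimated also by MCMC.

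A random intercept is named only in Precision of Estimates and Statistical Power, where the calculation is "for a design with a level-1 predictor variable, a random intercept, and no other random effects".

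The documents do not say:
- what counts as retained, or whether a client can re-enter care;
- how many retention measurements each person has. Monthly data are promised for a different outcome: "each positive individual from the study and from the CTC will have 18 monthly measurements of ARV refill status";
- what retention rate or difference is expected;
- whether the odds ratio will be person-specific or population-averaged.

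No time-to-event analysis, 18-month retention comparison or censoring rule is named.

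**The concern.** Retention differs from refill status. A client who misses one refill can collect the next. A client lost from care may stay lost, and the record is then a run of ones followed by a run of zeros. Given the person's intercept, the logistic model treats the months as independent. It can reproduce such runs only by making people differ enormously, that is, through a very large random-effect variance. The couple-versus-routine coefficient is expressed on that stretched scale.

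The effect of dyadic care on retention is a named part of Aim 2. An odds ratio several times the ordinary one, with a very wide sampling range at about 50 couples, could be read as a much larger benefit than the difference in the proportion retained.

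**Working it through.** **The plan's own figure.** The only model-based power statement uses 50 individuals, 3 occasions and ICC 0.50: 150 / (1 + (3 − 1) × 0.50) = 75, as stated. With 75 effective observations, power 0.80 at OR 4.26 is reproduced closely: 30% v 64.6% with continuity correction needs 76. That calculation is for a level-1 predictor. The retention contrast is at level 2 and has no power statement.

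**Inputs.** From the documents: binary repeated outcome, person-level group indicator, mixed model. Assumed, because not given: 18-month retention rates, a 10-point difference, 18 or 3 checks, one-way loss at constant hazard, random intercept only, no time term.

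**Model.** logit P(retained in month j | u) = b0 + b1 × couple + u, with u ~ N(0, s²). With T checks and end-of-study retention r, S(t) = r^(t/T). The probability of exactly k retained months is S(k) − S(k+1) for k < T, and r for k = T. The likelihood was integrated numerically and fitted to these expected frequencies with equal groups.

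| Retention, couple v routine | Ordinary OR at 18 months | Hazard ratio of loss | OR, 18 checks (s; latent ICC) | OR, 3 checks |
|---|---|---|---|---|
| 60% v 50% | 1.50 | 0.74 | 2.9 (4.5; 0.86) | 2.4 |
| 70% v 60% | 1.56 | 0.70 | 3.7 (5.2; 0.89) | 2.9 |
| 80% v 70% | 1.71 | 0.63 | 5.9 (5.9; 0.91) | 4.15 |
| 90% v 80% | 2.25 | 0.47 | 19 (6.9; 0.93) | 10 |

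For 80% v 70%: ordinary OR = (0.80/0.20)/(0.70/0.30) = 1.71; hazard ratio = ln 0.80 / ln 0.70 = 0.63; latent ICC = 5.89²/(5.89² + 3.29) = 0.91.

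**Check by hand.** Averaged over the 18 checks, retention is 89.1% v 83.3%, a marginal OR of 1.64. The usual conversion multiplies the log OR by √(1 + 0.346 s²) = √(1 + 0.346 × 34.7) = 3.6, and 1.64^3.6 ≈ 5.9. This agrees with the fit: the inflation comes from the variance.

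**Sensitivity, 80% v 70%, 18 checks.**
- Timing of loss, S(t) = r^((t/18)^k): 16.5 if early (k = 0.5), 3.6 if late (k = 2).
- Monthly return of lost clients: 2% gives 5.1, 5% gives 4.2, 10% gives 3.3, 20% gives 2.4, 30% gives 2.0.
- At the ICC of 0.50 in the power section (s² = 3.29): 1.71^√(1 + 0.346 × 3.29) = 1.71^1.46 = 2.2.
- With a linear time term and strictly one-way loss, the random-effect SD ran to extreme values and no usable finite OR was obtained.

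**Finite samples.** 50 couples, one-way loss, 18 checks, 200 runs per row. The last column comes from runs with 70% retention in both groups.

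| Comparison clients | Median OR (80% v 70%) | 10th–90th percentile | Rejection under equal retention |
|---|---|---|---|
| 50 | 5.8 | 0.8–57 | 5.0% |
| 200 | 7.8 | 1.4–49 | 5.5% |
| 500 | 5.5 | 1.6–27 | 6.0% |

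The Monte Carlo standard error at 5% is √(0.05 × 0.95/200) = 1.5 points, so the level is not visibly disturbed. Power was 0.20, 0.36 and 0.35, against 0.21, 0.31 and 0.33 for a simple comparison of 18-month proportions in the same runs.

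**The case against.** The strongest reply is that the inflation rests on premises the documents do not supply. Retained is undefined. If it means attendance in a given month, clients can return and the person-specific odds ratio moves towards the ordinary one. The random-intercept structure is taken from a power paragraph about another kind of predictor, while the Analysis Plan says that distributions will be inspected, trajectories plotted, and fixed and random effects chosen by model building. The study is described as exploratory and promises descriptive statistics. For retention the text speaks of testing a difference, not of centring the report on odds ratios. All of this stands and limits the size of the point. It does not remove it: inspecting plots does not name a retention estimand, the freedom to use other specifications is stated for refill status, and choosing the summary after seeing the data is itself a weakness.

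Three stronger readings are tempting and are not supported.
- A reader might infer that a 10-point difference becomes an odds ratio above 6. At 80% v 70% with monthly checks it is 5.9. Larger values need higher retention or earlier loss, and smaller ones follow from fewer checks, later loss or re-entry.
- A reader might infer that the model needs complete 18-month records and would drop clients with fewer. The Analysis Plan says that these models accommodate differing numbers of measurements, plans to use all available data where little is missing, and otherwise names multiple imputation or pattern mixture models.
- A reader might infer that the odds ratio has no clinical meaning or that the test is invalid. A person-specific odds ratio is a legitimate but different quantity, and the test keeps its level.

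**Conclusion.** The point holds in conditional form. The plan commits retention to a repeated binary mixed model with a log-odds contrast and leaves both the outcome and the reported summary undefined. If loss is close to permanent and the model is a random intercept without time, an ordinary odds ratio of 1.5 to 2.3 becomes a person-specific one of about 2.9 to 19 with monthly checks, or 2.4 to 10 with three, for routine-care retention of 50% to 80%. With about 50 couples the estimate is also very unstable. With substantial re-entry most of the inflation goes: 2.4 against 1.7 at 80% v 70% with 20% monthly return. The fault lies in the size, stability and interpretation of the estimate, not in the p-value.

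**What to change.** In the AIM 2 text:
- Define loss from care by a stated gap rule applied in the same way to both groups, and say how re-entry is treated.
- Make the difference in 18-month retention, with 95% CI, the main retention result.
- Support it with Kaplan-Meier curves and a Cox or discrete-time hazard model, censoring at the data cut and at death or transfer where CTC2 records them. Say how any months affected by the pause in CTC2 extraction from 1 May 2020 are handled.
- Keep the repeated-measures logistic model for monthly refill. If it is also kept for retention, report marginal (population-averaged) probabilities beside the odds ratio.

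The cost is some rewording of the analysis plan. The clinical item under Measures already lists visit dates for participants and, in blinded form, for other CTC clients. Death and transfer dates are not in that list, so their availability in CTC2 has to be checked before the censoring rule is fixed.
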